Severe Acute Respiratory Syndrome Coronavirus 2 (SARS-CoV-2) testing strategy is essential for the diagnostic work up and screening during the coronavirus disease 19 (COVID-19) pandemic. Proper upper respiratory specimen collection is the most critical step in the diagnosis of SARS-CoV-2 virus in public settings and standard sample guidelines are recommended⁽¹⁾. An oropharyngeal swab (OPS) specimen is the preferred sample in many countries, either alone or combined with nasal swab^(2, 3). However, there is a great variability in the diagnostic accuracy for OPS with a 95% confidence interval from 52-100% reported in systematic reviews^(4, 5) and The Infectious Diseases Society of America therefore do not recommend OPS for SARS-CoV-2 testing⁽⁶⁾. Many of the previous studies performing OPS also lack detailed description of the sample technique, which makes it difficult to compare the different diagnostic accuracy results. Currently, there are no standardized oropharyngeal sample guidelines, and some only collect specimen from the posterior oropharyngeal wall while other recommend also to include a swab of the palatine tonsils for SARS-CoV-2 testing (Figure A). The Danish Health Authority advised to avoid the palatine tonsils in the oropharyngeal swab in the beginning of the COVID-19 pandemic, but later changed their recommendation so it was up to the individual testing center to decide⁽⁷⁾. However, studies suggest that the palatine tonsils could have a tissue tropism for SARS-CoV-2 which may improve the SARS-CoV-2 detection during sampling⁽⁸⁾. This may explain the variation of sensitivity reported, but no clinical studies have explored the differences between the two sample techniques. We therefore plan to conduct a randomized clinical trial to compare an oropharyngeal swab with or without the palatine tonsils.

[figure not shown]

FIGURE A. Image A. Anatomic visualization of the posterior oropharyngeal wall (green) and palatine tonsils (pink). Image B. Oropharyngeal swab including the posterior oropharyngeal wall and palatine tonsils. Image C. Oropharyngeal swab including the posterior oropharyngeal wall, but avoiding the palatine tonsils.

Research question

In a cohort of individuals tested for COVID-19 at a public test center, what is the sensitivity of an OPS sample, including the palatine tonsils, compared to only swabbing the posterior oropharyngeal wall in molecular detection of SARS-CoV-2?

Methods

We will conduct a randomized, controlled study to compare the molecular detection rate of SARS-CoV-2 by an OPS performed from the posterior oropharyngeal wall and the palatine tonsils (intervention group) or the posterior oropharyngeal wall only (control group). This trial is approved by the Danish Data Protection Agency (Protocol No. P-2022-803) and reported to the Regional Ethics Committee of the Capital Region of Denmark who considered it exempted from further processing (Protocol No. H-22022937). The protocol was registered with the ClinicalTrials.gov database (NCT05611203). A grant was received from the Novo Nordisk Foundation (Grant number NNF21SA0069151) without influence on study design, data collection, data analysis, writing of the report, and the decision to submit the results for publication.

Study setting

Participants will be enrolled in a free public Covid-19 Testcenter in Valby and Hillerød, Capital Region, Denmark starting from November 2022. All samples will be sent for molecular testing at Statens Serum Institut and data analysis will be performed at Rigshospitalet.

Only special trained healthcare workers at Valby and Hillerød Testcenter will collect specimens from the participants enrolled in the study. Before enrollment, all healthcare workers will receive training and a competency-based assessment of their skills (appendix 1).

Eligibility criteria

Individuals with or without symptoms of upper respiratory tract infection age 18 or above who visit Valby or Hillerød Testcenter for RT-PCR-testing for SARS-CoV-2 will be offered participation in the study. Participation is voluntary, and participants are required to provide oral and written consent to participate prior to entering the study (appendix 2).

The exclusion criteria are individuals with a tracheostomy, laryngectomy, or prior oropharyngeal cancer surgery that would make the OPS difficult. Further, individuals without a Danish civil

registration number (CPR) will be excluded to participate. Individuals who are not included in the study will have the standard oropharyngeal swab performed in the test center.

[figure not shown]
The same individual will only be allowed to participate in the study once. If a participant is enrolled in the study more than once, only the first enrollment (or the first positive test case) will be included, while the following test results will be excluded from the statistical analysis.

Randomization to intervention and control group

After enrollment, the participants will be randomized in a 1:1 ratio having either oropharyngeal swab performed including the posterior oropharyngeal wall and both palatine tonsils (intervention group) or only including the posterior oropharyngeal wall and avoiding the palatine tonsils (control group), see Figure B.

A block randomization list was generated by [name] using an online randomization software⁽⁷⁾ afterward uploaded to REDCap. The randomization group will be disclosed in connection with trial registration in REDCap using the REDCap “randomize” function. The oropharyngeal sample will afterward be performed by the trained healthcare workers with or without the palatine tonsils depending on the randomization to either the intervention or control group.

Figure B. Study flowchart.

The swabs will be placed in separate tubes dry and sent to the clinical microbiology laboratory for detection of SARS-CoV-2 by single-target RT-PCR at Statens Serum Institute. Samples with viral cycle threshold (Ct) values below 38 are considered positive, 38-40 inconclusive and above 40 negative⁽⁸⁾.

All participants are required to fill out a survey on-site about their reason for being tested, prior Covid-19 infection(s), vaccinations status, symptoms, and if any prior tonsillectomy has been performed (appendix 2).

All healthcare workers participating in the data collection have been given a unique ID which will be registered for each OPS performed in the study. Further, the healthcare worker will also be asked to rate the Mallampati score of the participants including in the study (appendix 5).

All data will be documented on-site in a secure web database (REDCap, appendix 3).

Outcomes

The primary outcome will be reported as:

- SARS-CoV-2 RNA by RT-PCR test result (positive, negative, inconclusive)

The secondary outcome will be reported as:

- SARS-CoV-2 RT-PCR cycle threshold (Ct) value
- Test discomfort on a 11-point NRS-scale
- Development of COVID-19 disease after testing
- SARS-CoV-2 detection rate for each healthcare worker
- Mallampati Score of participants being tested

Sample size

Based on a SARS-CoV-2 test positive proportion on 13% in the Danish capital region the last week of October 2022, we expected proportion of positive to increase to about 20% during the following study period⁽⁹⁾. The power calculation was based on an expected improvement in diagnostic accuracy of 25% by including the palatine tonsils in the oropharyngeal specimen collection compared to a sample without the tonsils. We therefore estimated that a sample of 2,188 participants (with about 438 with SARS-CoV-2 infection) would provide the trial with 80% power at a 5% significance level with an expected test positive proportion of 20% for SARS-CoV-2

among the participants tested ⁽¹⁰⁾. As we expect about 10% missing due to dropout and missing data, we aim to include 2,407 participants in the study. All individuals entering the testing facility who meet the eligibility criteria are offered to participate in the study. We expect about 300-700 tests performed at both COVID-19 test centers each day and an assumed participation at 10-30%. We therefore expect to complete the study within two-three months.

Statistical analysis

A study participant is considered to have a SARS-CoV-2 infection if the oropharyngeal sample is RT-PCR positive (reference standard). Participants with an inconclusive RT-PCR test result will be included in the analyses as a negative test result following an intention-to-diagnose approach⁽¹¹⁾. Differences in the proportion of SARS-CoV-2 positive tests between the intervention and the control group will be compared using binary logistic regression using test center as fixed effect and a generalized estimating equation to adjust for clustering of data within the healthcare workers performing the sample. The difference in SARS-CoV-2 detection rate between healthcare workers will also be reported separately to estimate the inter-person variance. The Ct values from positive RT-PCR samples and the NRS discomfort scores will be compared using a general linear model with mixed effects (Ct) and GEE models (NRS discomfort). The 95% confidence intervals (CI) will be presented. Categorical data will be summarized with number and percentage while continuous data will be summarized by mean and standard deviation. We will not perform tests of statistical significance for baseline characteristics. 5% significance level was applied. Statistical Analysis Software ver. 9.4 (SAS Institute, North Carolina, U.S.) was used for the statistical analyses.

Planned subgroup analyses

We planned to do a sensitivity analysis using a lower cycle threshold (Ct) < 25 for positive SARS-CoV-2 definition to explore the consequences of a higher test specificity for the SARS-CoV-2 detection rate between specimen types. We also plan to estimate the sensitivity and specificity using Bayesian latent class analysis for accounting for an imperfect reference standard. Further, we planned to do subgroup analyses exploring the distribution of positive test results for participants stratified by symptoms, previous COVID-19 infection, vaccinations status, prior

tonsillectomy and Mallampati score. To explore a potential bias from the distribution of the inconclusive test results, we excluded the inconclusive results in a subgroup analyses.

Quality assurance

All the healthcare workers who will be including participants for this study will be trained and have at least three months prior experience in oropharyngeal swabs. Further, they will complete a special standardized training- and certification program taught by a board-certified otorhinolaryngologist to ensure all healthcare workers perform the same technique on the participants in the intervention and control group. A two-hour long training session will cover the theoretical and practical part of oropharyngeal sample techniques and the study design with following elements:

- A walk-through of the practical study setup and how participants are enrolled, and diagnostic interventions are performed
- Theory on oropharyngeal swabbing including upper airway anatomy and anatomical variations/Mallampati Score.
- Practical exercises in oropharyngeal swab technique.

Checklists outlining the two different sampling techniques for oropharyngeal swabs with and without palatine tonsils, respectively, will be used to assess the swab performance of all the healthcare workers by a board-certified otolaryngologist or special trained nurse before study enrollment (see appendix 1).

An on-site healthcare professional is in charge of internal daily quality assurance ([name]).

Follow-up

The participants enrolled in the study will be asked to agree to be contacted in case of a positive test result. About one month after a positive test results the participants will receive an online questionnaire or phone call to follow up. The follow-up questions can be found in appendix 3.

Ethics and safety considerations

The purpose of the study is to compare the detection rate of the two different sampling techniques. Both techniques used in this study are implemented in the Danish healthcare system and are thus considered reliable methods for detecting and diagnosing infection with SARS-CoV-2. The study protocol is approved by the local ethical committee and the participants of the study are not subject to any adverse intervention and are put at no greater risk than the risk associated with a regular SARS-CoV-2 test.

Data plan

Data will be collected on-site in the secure database REDCap. Identifiers such as CPR-number, healthcare worker-ID and sample-ID are registered directly in the database for each new participant. The survey will be marked with a REDCap-ID allowing the research group to later match records with the physical surveys. Surveys are filled out on site by the participants and healthcare workers and stored in accordance with GDPR-legislation until data entry. Data entry will be done either by on-site healthcare workers continuously throughout the data collection period or by the research group once data collection is completed. No data analysis will be conducted before data collection is completed.

Declaration of interests

The authors have no competing interests to declare.

Access to data

The anonymized data will be made publicly available through an open access database after publication.

Appendices

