1.2 Adherence and Protocol deviations

Definition of adherence to the intervention

Adherence is defined as participants who has a full registration of identification number (CPR number), test center site for collection of specimen and randomization to control or intervention group. Further, the participants need to complete the OPS specimen collection send for molecular testing.

Compliance is assessed based on the number and percent of subjects who have correct registration information and representative samples for RT-PCR.

Description of adherence

The adherence to the intervention will be summarized in the study flowchart and number and “% compliance” will be summarized.

Definition of protocol deviations for the trial

The participants will be excluded from final analysis if one or more of the following deviations from the testing protocol was found:

Missing identification number (CPR number), no registered test center sites or no randomization (intervention or control) registered.

Missing RT-PCR result

Description of which protocol deviations will be summarized

The number and type of protocol deviation will be registered, and number of participants removed will be summarized in figure with study flow.

2. Trial Population

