2.2 Eligibility

All individuals being 18 years or older will be invited to participate in the SAMPLE trial. The same individual will only be allowed to participate in the study once.

The exclusion criteria were individuals with a tracheostomy, laryngectomy, or prior oropharyngeal cancer surgery without a Danish civil registration number (CPR)

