2.3 Recruitment

A trial flow diagram will be used to summarize the number of included participants with information about:

- Total number of Covid-19 tested individuals during the study period
- Number of participants lost to identify / registrar
- Number of participants excluded from final analyses due missing test results

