3.1 Outcome definitions

The primary outcome:

- The proportion of positive SARS-CoV-2 RNA samples by RT-PCR for intervention and control group

The secondary outcome:

- SARS-CoV-2 RT-PCR cycle threshold (Ct) value
- Test discomfort on a 11-point NRS-scale
- Development of COVID-19 disease after testing
- SARS-CoV-2 detection rate for each healthcare worker
- Mallampati Score of participants being tested

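### The rule for people enrolled twice lets the test result decide which randomised record is analysed; the effect is probably small and is easily removed

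*Combined protocol and SAP*

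**What the plan says.** Participation is meant to happen once. SAP 2.2 (Eligibility) states: "The same individual will only be allowed to participate in the study once". The protocol's Eligibility criteria section says the same but also provides for failures of the rule: "only the first enrollment (or the first positive test case) will be included", "while the following test results will be excluded from the statistical analysis".

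The SAP gives no rule for repeats that occur anyway:

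- SAP 1.2 opens its list with "The participants will be excluded from final analysis if one or more of the following deviations from the testing protocol was found". The list covers an absent CPR number, test centre, allocation or RT-PCR result. Repeat enrolment is not on it.
- SAP 2.3 lists the flow-diagram items, such as "Number of participants excluded from final analyses due missing test results". Repeat enrolments are not among them.

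The primary outcome in SAP 3.1 is "The proportion of positive SARS-CoV-2 RNA samples by RT-PCR for intervention and control group", the same variable on which the parenthesis selects. The protocol's Statistical analysis section adds: "Participants with an inconclusive RT-PCR test result will be included in the analyses as a negative test result". The Data plan says: "No data analysis will be conducted before data collection is completed".

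**The concern.** If the first enrolment is positive, both criteria pick the same record. If every enrolment is negative or inconclusive, only the first criterion applies. They part when the first result is not positive and a later one is, and there the word joining them sets no order.

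On one reading the later positive replaces the earlier record. Because each enrolment is randomised 1:1, the replacement may sit in the other arm, so the outcome decides which allocation is analysed. Some replaced records could be missed infections, which are the events that separate the two swab techniques. Others could be true negatives before a new infection. One swab per visit cannot tell them apart.

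On the other reading the order is simply open, and would be settled after data collection, when results exist. Either way, two different data sets are allowed for the primary test, and a reader could not tell which had been used.

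**Working it through.** **Design figure reproduced.** Inputs from the protocol's Sample size section: 20% positive, 25% relative improvement (so 20% v 25%), 80% power, 5% significance. Two-sided testing is assumed.

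n per arm = [1.960·√(2·0.225·0.775) + 0.842·√(0.25·0.75 + 0.20·0.80)]² / 0.05² = (1.1575 + 0.4961)² / 0.0025 = 1,093.7, rounded up to 1,094. The total is 2,188, as stated.

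**Assumptions (the documents give no figures).**

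- Repeaters: 2% or 5% of persons, each with two independent 1:1 allocations and return independent of arm.
- Detection among the infected: 100% v 80%, or 75% v 60%. With prevalence 25% or 33.3%, both give 25% v 20%.
- Repeaters infected at the first visit: as others, 50%, or 0%. New infection before the second visit: 0%, 20%, or, in the 0% case, the general prevalence.

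**Worked case: 5% repeaters, half infected at first visit, 100% v 80%, no new infections.**

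1. First-enrolment rule. Intervention: 0.95·25% + 0.05·50% = 26.25%. Control: 0.95·20% + 0.05·40% = 21.00%. Risk ratio (RR) 1.250, odds ratio (OR) 1.339, risk difference (RD) 5.25 points.
2. Repeaters: 0.05·2,188 = 109.4. Infected: 54.7, of whom 27.35 were first in control. Missed there: 0.20·27.35 = 5.47.
3. At the second visit, 5.47·0.5·1.0 = 2.735 are positive in the intervention arm and 5.47·0.5·0.8 = 2.188 in control. Replaced: 4.92, of which 2.735 change arm.
4. First-positive rule. Intervention: (287.18 + 2.735)/(1,094 + 2.735) = 26.43%. Control: (229.74 + 2.188)/(1,094 − 2.735) = 21.25%. RR 1.244, OR 1.331, RD 5.18 points.

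**Other cases at 5% repeaters (first enrolment → first positive).**

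| Detection | Infected at first visit | New infections | Replaced | False negatives among them | RR | OR | RD, points |
|---|---|---|---|---|---|---|---|
| 100/80 | 50% | 0% | 4.9 | 4.9 | 1.250→1.244 | 1.339→1.331 | 5.25→5.18 |
| 75/60 | 50% | 0% | 12.0 | 12.0 | 1.250→1.245 | 1.336→1.332 | 5.13→5.16 |
| 75/60 | 50% | 20% | 19.4 | 12.0 | 1.250→1.244 | 1.336→1.333 | 5.13→5.21 |
| 75/60 | 0% | 33.3% | 24.6 | 0 | 1.250→1.247 | 1.328→1.329 | 4.75→4.94 |

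The upper count is 109.4·(1/3)·0.675 = 24.6, where 0.675 is the mean of 0.75 and 0.60. The lower count (2% repeaters, 100/80, prevalence as others, no new infections) is 43.76·0.25·0.5·0.20·0.9 = 0.98.

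**Scale of the OR shift.** At 25% v 20%, the standard error of the log OR is √(1/273.5 + 1/820.5 + 1/218.8 + 1/875.2) = 0.103. The largest move is ln(1.339/1.331) = 0.006, about 0.06 standard errors.

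**Significance, by simulation** (Wald test of the log OR, no clustering by healthcare worker).

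- No true effect: about 5.0% under each rule fixed in advance. The chance that at least one reading is significant is 5.2–5.6% with 2% repeaters and 5.4–5.9% with 5%. Separate simulations gave about 5.5% and 5.8%, and up to about 6.0%.
- Planned effect: the readings disagree on significance in 0.8–2.5% of trials (2% repeaters) or 1.5–3.8% (5%) when some repeaters are infected at the first visit. In the limiting case where none is (last table row, and the same case at 2%), a further run of 400,000 trials per setting gave about 3% and 5%.

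**The case against.** The strongest reply is that the main rule is the first enrolment, that the sentence goes on to drop later results ("while the following test results will be excluded from the statistical analysis"), and that nothing expressly removes an earlier negative. The parenthesis would then be loose wording and not a rule of replacement. This shows that replacement is not the only reading. It does not close the question: only one record may be included, so if the first positive is the one taken, the earlier negative must go. The later results could be those after the first enrolment or those after the first positive.

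Secondly, repeats should be rare. Participation is once only and CPR numbers go straight into REDCap. If returners joined again at the protocol's assumed 10–30% participation, 2% repeaters would need 7–20% of participants to return (2/30 to 2/10), and 5% would need 17–50%, with the once-only rule failing each time. That is a fair reason to treat 5% as a high assumption.

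Thirdly, a fixed rule of either kind does almost no harm, and nothing suggests that both versions would be run and the better one reported. The Data plan sentence guards against early looks and is not a fault; it shows only that an open choice would be made late. All of this stands and limits the weight of the point.

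Two smaller objections also stand. An inconclusive first result raises no separate problem, because its coding as negative does not say which record enters. SAP silence does not contradict the protocol; it leaves the unclear sentence as the only rule.

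**Conclusion.** The concern holds. The text sets no precedence between two criteria, one of which selects on the primary outcome and can change the arm analysed, and the SAP does not resolve it.

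The consequence is probably small. Under the assumed 2–5% repeaters, about half of the replaced records change arm. The RR falls from 1.25 to no lower than 1.242, the OR stays near 1.33, and the RD moves by at most 0.2 points. Type I error is not inflated by either rule fixed beforehand, provided return does not depend on arm. The modest inflation arises only if the reading is chosen with results in view.

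The repeat share, the detection rates and the new-infection rates are all assumptions. The case for changing the sentence is that the analysed record should follow from the first randomisation, and that this can be secured at almost no cost. It should be changed, but it does not threaten the trial.

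**What to change.** Delete the parenthesis about the first positive test. State instead: if a person is enrolled more than once, identified by CPR number, the first randomised enrolment is analysed whatever its result, and all later enrolments are excluded. Put the same sentence in SAP 2.2, add repeat enrolment to the exclusion list in SAP 1.2, and show the number of repeat enrolments by arm in the SAP 2.3 flow diagram. A first-positive version may be kept as a labelled sensitivity analysis.

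The cost is one sentence in the protocol and the SAP, one entry in the exclusion list and one line in the flow diagram. A few positives may be lost from the count, at most about 25 under the assumptions above.

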Appendix 2: Survey for participants

Survey to be filled out by participant

1. Are you vaccinated against COVID-19?

YES

NO

2. Have you previously been infected with COVID-19?

YES

NO

3. Please indicate your reason for getting tested today:

Symptoms

Close contact

Positive quick test

Screening

Test ahead of social gathering or nursing home visit

Other

If 'yes' to symptoms, which symptoms do you have?

Sore throat

Headache

Cough

Muscle and joint pain

Fever

Fatigue

Reduced sense of smell or taste

If "yes" to symptoms, for how many days have you had symptoms?

Indicate number of days: _____ day(s)

4. Have you had your tonsils removed??

YES

NO

5. On a scale from 0-10, how uncomfortable was today's test for COVID-19?

No discomfort

Worst possible discomfort

To be filled out by personnel:

REDCap ID: _____

Personnel ID: _____

Participant's Mallampati score:

1

2

3

4

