Appendix 5: Mallampati score

Klasse 1: Udsyn til den bløde gane, drøbelen, mandler og ganebuer,

Klasse 2: Udsyn til den bløde gane og drøbelen samt delvist til mandlerne.

Klasse 3: Udsyn til den bløde gane og den øverste del af drøbelen.

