2.5 Baseline patient characteristics

List of baseline characteristics for participants:

Measure	Outcome	Description
Demographic data	Age and gender	Data from the Danish civil registration number
Questionnaire	Test reason, symptom description, vaccination status, prior SARS-CoV-2 infection, prior tonsillectomy	Questionnaire registered in RedCap
NRS-scale	Discomfort score for OPS specimen collections	11-item measure of test-related discomfort answered immediately after testing
Mallampati score	A visual assessment of the distance from the tongue base to the roof of the mouth of the participants	4-item measure of amount of space in the mouth to reach the oropharynx assessed by the healthcare workers

Categorical data will be summarized with number and percentage while continuous data will be summarized by mean and standard deviation. We will not perform tests of statistical significance for baseline characteristics.

3. Analysis

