We planned to do a sensitivity analysis using a lower cycle threshold (Ct) < 25 for positive SARS-CoV-2 definition to explore the consequences of a higher test specificity for the SARS-CoV-2 detection rate between specimen types. We also plan to estimate the sensitivity and specificity using Bayesian latent class analysis for accounting for an imperfect reference standard. Further, we planned to do subgroup analyses exploring the distribution of positive test results for participants stratified by symptoms, previous COVID-19 infection, vaccinations status, prior tonsillectomy and Mallampati score. To explore a potential bias from the distribution of the inconclusive test results, we excluded the inconclusive results in a subgroup analyses.

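### The plan does not require the Mallampati score to be rated before allocation, so a baseline descriptor and exploratory subgroup factor could be influenced by the arm

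*Combined protocol and SAP*

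**What the plan says.** **Sequence.** In the protocol section on randomisation, "The randomization group will be disclosed in connection with trial registration in REDCap using the REDCap “randomize” function". Then "The oropharyngeal sample will afterward be performed by the trained healthcare workers with or without the palatine tonsils depending on the randomization". No blinding of the worker is described, and none is possible for the person who takes the swab.

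**Rater and form.** The same section assigns the rating to the healthcare worker: "Further, the healthcare worker will also be asked to rate the Mallampati score of the participants including in the study (appendix 5". SAP 2.5 agrees and describes the score as a "4-item measure of amount of space in the mouth to reach the oropharynx assessed by the healthcare workers". In Appendix 2 the score sits in the personnel block at the foot of the sheet, beneath the participant item "On a scale from 0-10, how uncomfortable was today's test for COVID-19", which SAP 2.5 says is answered straight after the test.

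**Definition.** Appendix 5 (in Danish) gives class 1 as a view of soft palate, uvula, tonsils and palatal arches. The next class reads "Klasse 2: Udsyn til den bløde gane og drøbelen samt delvist til mandlerne", so the tonsils are seen only in part. Class 3 mentions the soft palate and the upper part of the uvula, not the tonsils.

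**Use.** The score is a baseline characteristic (SAP 2.5), a secondary outcome ("Mallampati Score of participants being tested", SAP 3.1 Outcome definitions and the protocol's Outcomes) and a subgroup factor: positive results are "stratified by symptoms, previous COVID-19 infection, vaccinations status, prior tonsillectomy and Mallampati score".

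**The concern.** A subgroup comparison keeps the protection of randomisation only if the factor could not have been changed by the allocation. Here the person who assigns the class knows the arm, and may have just brushed both tonsils or deliberately avoided them. The class 1/2 boundary turns partly on that same structure, so the same throat might be classed differently by arm.

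If that happened, and if positivity differed between classes, the arms would not be comparable within a recorded class. A measurement artefact could then be read as the tonsil swab working differently by throat anatomy. An interaction test would not repair this, because the strata themselves would be distorted. The baseline table could also show an imbalance that randomisation did not produce.

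Listing the score as baseline factor and outcome at once adds to the ambiguity: the first role assumes the arm cannot affect it, the second invites a comparison by arm. SAP 3.1 names no analysis for it as an outcome.

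**Working it through.** **1. Is a rating before allocation secured?** No. Disclosure comes before the swab, the rater is the healthcare worker, and the rating box is below a post-swab item. Nothing asks for the rating before allocation or by someone unaware of the arm. The baseline label does not settle it, because SAP 2.5 also lists the post-swab discomfort score as baseline.

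**2. Could the arm influence the class?** The two checklists in Appendix 1 differ only at item 7, where one adds both palatine tonsils. Visualisation of the back wall, spatula and phonation are identical. The route is therefore attention to the tonsils, not a different view.

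**3. Scale from the plan's own figure.** For 20% v 25% (a 25% relative gain), two-sided 5%, 80% power:

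n per arm = [1.96·√(2·0.225·0.775) + 0.8416·√(0.20·0.80 + 0.25·0.75)]² / 0.05² = 1,094, or 2,188 in total, as stated. I use 1,094 per arm below.

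**4. Illustration at the class 1/2 boundary.** Every input here except the 1,094 is assumed. There is no true arm effect, and all participants are class 1 or 2. Let w be the true class 1 share, a and b the positivity in classes 1 and 2, and m the fraction of true class 2 recorded as class 1 in the tonsil arm only.

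- Recorded class 1 share in the tonsil arm: s = w + (1−w)m
- Its positivity: c = [wa + (1−w)mb]/s
- False class 1 difference: c − a
- SE = √[c(1−c)/(1094s) + a(1−a)/(1094w)]

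Example with w = 0.30, a = 0.25, b = 0.15, m = 0.10: s = 0.37; c = (0.075 + 0.0105)/0.37 = 0.231; difference −1.9 points; SE 3.2 points.

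| w | a / b | m | s | False difference (points) | SE (points) |
|---|---|---|---|---|---|
| 30% | 22% / 18% | 10% to 30% | 37% to 51% | −0.8 to −1.7 | 3.1 to 2.9 |
| 30% | 25% / 15% | 10% to 30% | 37% to 51% | −1.9 to −4.1 | 3.2 to 2.9 |
| 50% | 22% / 18% | 10% to 30% | 55% to 65% | −0.4 to −0.9 | 2.4 to 2.3 |
| 50% | 25% / 15% | 10% to 30% | 55% to 65% | −0.9 to −2.3 | 2.5 to 2.4 |

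If a = b the false difference is zero. The worst corner, −4.1 points, is 1.4 SE. A 5% interaction test on the ratio of class-specific risk ratios would have an expected z of 0.10 to 0.98 and reject in about 5% to 17% of trials, against a nominal 5%.

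**5. Illustration at the class 2/3 boundary.** Pool classes 1–2 as a good view. Assume 60% good view, control positivity 24% (good) and 14% (poor), and a true ratio of 1.25 in both. Both inputs are consistent with the plan: 0.6·24% + 0.4·14% = 20%, and 1.25 is the planned gain. A fraction m moves from poor to good in the tonsil arm and from good to poor in the control arm.

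- Good stratum ratio = 1.25·(0.6·0.24 + 0.4m·0.14)/(0.6 + 0.4m)/0.24
- Poor stratum ratio = 1.25·0.14/[(0.4·0.14 + 0.6m·0.24)/(0.4 + 0.6m)]

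At m = 10% these are 1.22 (95% CI about 1.01 to 1.46) and 1.14 (0.85 to 1.54), with interaction z 0.35. At m = 20% they are 1.19 and 1.07, with z 0.57. The test would reject in about 6% and 9% of trials.

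**6. Would a by-arm table show it?** In step 4 the class 1 share differs between arms by s − w, which is 5 to 21 points. Its SE is √[s(1−s)/1094 + w(1−w)/1094], about 2.0 to 2.1 points. The gap is thus 2.3 to 10.2 SE, much plainer than the distortion it causes.

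**The case against.** **Timing.** A reader might infer that the rating is made after the swab as a matter of fact. No sentence says so. The flowchart is not reproduced in the text available, and the order of fields in Appendix 3 is not a clock: the civil registration number follows randomisation there, and the Data plan allows paper surveys to be entered later. What stands is that the plan does not secure an earlier rating and its form points to a later one.

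**The rest of the survey.** A reader might also infer that participant items 1–4 are completed after the swab because they share the sheet. The documents do not support this. SAP 2.5 gives post-test timing only for the discomfort score, and a sheet can be started before the swab and finished after it.

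**Mechanism.** Both arms use the same viewing steps, and avoiding the tonsils may itself require seeing them. All workers receive the same training, which covers Mallampati. This stands as mitigation, but it does not blind the rater.

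**Size.** It is tempting to say that a false interaction will appear. The calculations do not bear that out: the expected interaction z stays below 1 throughout. The step 5 model also works at a boundary that Appendix 5 separates by the uvula as well as the tonsils, and it assumes opposite shifts in the two arms. The analysis is exploratory and no interaction test is planned. All this stands, and it sets how much weight the point deserves.

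**Conclusion.** The point holds as a risk that the plan leaves open. The rating by an unblinded worker is not required before allocation, the class 1/2 boundary refers to the tissue that defines the arms, and the score is used as a baseline and subgroup factor. Bias needs two conditions together: rating that differs by arm, and positivity that differs between classes. The documents show neither.

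The exposure is the exploratory Mallampati subgroup and the baseline table, plus the score's redundant listing as an outcome. A reader should not extend it to the main result: the whole-arm comparison does not use the score, and SAP 3.1 adjusts only for test center and healthcare worker.

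Under the assumed inputs the subgroup distortion is mostly under one standard error, and 1.4 in the most extreme case. If some participants are in classes 3 or 4, the class 1 groups are smaller and sampling error is larger still. This is a cheap improvement worth making, not a threat to the trial.

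**What to change.** 1. Have the healthcare worker rate and record the Mallampati score before the REDCap randomise step. Paper is enough, and live entry is not needed.
2. Delete the score from the secondary outcomes in the protocol and SAP 3.1. Keep it as a baseline descriptor and subgroup factor.
3. If the order cannot change, or enrolment is already complete, state in the SAP that the score was rated after allocation by a worker who knew the arm (or that the timing was not controlled). Report the class distribution by arm, and do not interpret the subgroup as evidence of effect modification.

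Cost: a brief mouth inspection moves ahead of randomisation at centers expecting 300–700 tests a day, and a few people may be rated but not randomised. The form needs one box moved and the SAP a line or two. No new data or visits are needed. The fallback costs only text and one by-arm tabulation.
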